8.1.5 Demographic and Baseline Characteristics

Baseline characteristics will be summarized in Baseline Characteristic summary table for two treatment arms

8.1.6 Efficacy Analysis

The primary objective of this study is to compare the rate of MRD at 12 months between the two arms. Because this is a proof of concept trial rather than a confirmatory trial, the comparison will be made using a one sided test at the 10% significance level. This comparison will be performed using (i) a chi-square or Fisher's exact test comparing the two treatment arms, and (ii) a Cochran Mantel-Haenszel (CMH) test stratified by VGPR status and risk factors vs. no risk factors. We anticipate 20-30% of pts will be high risk and 20-40% will be in less than a VGPR at study entry. Therefore, in the event of small stratum sizes (<5 per stratum in either treatment arm), we will conduct an exact logistic regression analysis in place of the CMH test (Hirji, Mehta, and Patel, et al., 1987).

Secondary objectives include the overall response rate, defined as at least a partial response to therapy (>PR), at least VGPR (>VGPR) and at least nCR rate (>nCR), CR, and sCR rates, time to progression, duration of response, and progression-free and overall survival. The rate of overall response will be reported along with its exact 95% binomial confidence interval. Time to event endpoints will be estimated using the product-limit method of Kaplan and Meier. Follow-

up time for these endpoints will be calculated from the date of randomization. For time to progression, patients that do not experience progression during follow-up will be censored on the date of their last clinical examination. Duration of response will be assessed conditional upon achieving at least a partial response. Follow-up time for this endpoint will be calculated from the date of the clinical examination, which confirmed the response, until the date of disease progression, or censoring at the date of last clinical follow-up. For progression-free survival, follow-up time will continue from the date of randomization until the date of documented disease progression or death. Patients who do not reach either milestone during follow-up will be censored on their date of last clinical assessment.

Correlative biomarkers will be assessed for association with response in the experimental arm using nonparametric tests given the relatively small number of responders anticipated (20%). A Wilcoxon rank-sum test will be used to compare baseline (pre-treatment) biomarker levels in the responders vs. non-responders.

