8. STATISTICAL AND QUANTITATIVE ANALYSES

8.1 Statistical Methods

A total of 60 patients will be enrolled in a 1:1 ratio stratified according to level of response (<VGPR vs \geq VGPR) and presence or absence of at least one poor prognostic risk factor (Yes to at least one cytogenetic risk factor including del-13 or hypodiploidy by karyotyping, or any of t(4;14), t(14;16), t(14;2), del17p, 1q21 gain by FISH. The primary objective of this study is to compare the rate of MRD at 12 months between the two arms. Because this is a proof of concept trial rather than a confirmatory trial, the comparison will be made using one-sided test at 80% power and at most 10% type I error. The outcome will be considered promising and warrant evaluation with phase III trial if MRD negative disease is 20% higher in the experimental arm vs. the control arm. This assumption is based on the following data:

- 1) While it is well established that CR rate may increase over time post-transplant, even without any maintenance (in the IFM study, at randomization to lenalidomide maintenance or placebo 5% and 8% of patients were in CR, but ultimately 29% and 27%, respectively achieved CR; Attal et al, N Eng J Med, 2012), the conversion to CR on lenalidomide maintenance in patients with established persistent measurable disease is expected to be less than 5%
- 2) CR rate to lenalidomide alone is estimated < 5% in newly diagnosed myeloma (Rajkumar et al, Blood 2005).
- 3) While there is not published data on the rate of conversion from less than MRD-negative to MRD-negative disease while on lenalidomide maintenance, it is estimated that only a small proportion of patients on lenalidomide arm (which we estimate to be < 5% and/or not to be clinically significant) will convert to MRD-negative status because of delayed effect of transplant and/or lenalidomide treatment.
- 4) Based on experience from the CRd trial ([name] et al, ASCO 2013), approximately 20% of patients have a potential to convert from less than MRD-negative to MRD-negative disease between 8 and 20 months (1-year) of the CRd treatment.

Together, these observations provided rationale for 12 months of duration of treatment and statistical design: an increase of the rate of MRD-negative disease by 20% - 28% in the experimental arm versus control arm was used for calculation of sample size (as for example 26.7 % rate in the experimental arm and 5% in control arm).

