8.1.1 Determination of Sample Size

A total of 60 patients (30 per arm) is based on the assumption that the rate of MRD negative disease that is approximately 20% higher in the experimental arm vs. the control arm will be considered promising for further evaluation. Because this is a proof of concept phase II randomized trial rather than a confirmatory trial, the comparison will be made using a one-sided test at 80 % power and at most 10% type I error. Table 8.1 below shows the detectable difference depending on the control rate. Boldfaced figures are values assumed most likely based on the literature and previous studies. Calculations are based on a Cochran-Mantel-Haenszel test with continuity correction.

Table 8-1 Detectable increases in the rate of MRD with 80 %power (one-sided $\alpha=0.10$)

Control Arm	Experimental Arm	Difference
2.5%	21.8 %	19.3 %
5.0%	26.7 %	21.7 %
10.0%	35.5 %	25.5%
15.0%	42.4%	27.4%
20.0%	48.1 %	28.1 %

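### Section 8.1.6 leaves the unstratified primary test open between one that breaks the 10% limit and one that is very conservative; naming Boschloo's test keeps the limit and adds about 4 to 6 points of power

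*Combined protocol and SAP*

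**What the plan says.** Section 8.1.1 sets the operating characteristics: "the comparison will be made using a one-sided test at 80 % power and at most 10% type I error". It fixes 30 patients per arm and states that "the rate of MRD negative disease that is approximately 20% higher in the experimental arm vs. the control arm will be considered promising". Table 8-1 in that section lists, for control rates from 2.5% to 20%, the experimental rate detectable with 80% power, and attributes the calculation to a continuity-corrected Cochran-Mantel-Haenszel (CMH) test. Section 8.1 gives the working example: "26.7 % rate in the experimental arm and 5% in control arm". It also expects few conversions on lenalidomide alone: "which we estimate to be < 5% and/or not to be clinically significant".

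Section 8.1.6 repeats the level ("the comparison will be made using a one sided test at the 10% significance level") and then names the tests. For the unstratified comparison: "This comparison will be performed using (i) a chi-square or Fisher's exact test comparing the two treatment arms". Alongside it stands (ii), a CMH test stratified by response and risk group, with exact logistic regression as the replacement if strata are small. Nothing says which of the two tests under (i) applies, or whether the chi-square test carries a continuity correction.

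**The concern.** With 30 per arm and perhaps zero to three control conversions, the tests that Section 8.1.6 allows can disagree on the same data. Take 3 conversions in the experimental arm and none in the control arm. The uncorrected chi-square gives z = 0.100 / sqrt(0.05 x 0.95 x 2/30) = 1.78, above the one-sided 10% critical value of 1.28. Fisher's test gives C(30,3)/C(60,3) = 4060/34220 = 0.119, which is not significant.

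Two things are at stake. If the uncorrected chi-square is used, the stated limit on type I error is not kept. If Fisher's test is used, the limit is kept with a wide margin, and power is lost that another valid exact test would recover from the same 60 patients. Leaving the choice open also allows it to be made after the counts are known.

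**Working it through.** **Inputs.** 30 per arm and a one-sided level of 0.10 (Sections 8.1.1 and 8.1.6); the rate pairs of Table 8-1; the 20-point target over a 5% control rate (Sections 8.1 and 8.1.1).

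**Method.** Let X and Y be the conversions in the control and experimental arms, binomial with n = 30 and rates pC and pE. For a test with rejection region R,

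Pr(reject) = sum over (x, y) in R of b(x; 30, pC) x b(y; 30, pE),

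taken over all 31 x 31 = 961 outcomes. Type I error sets pC = pE. The regions are:

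- Uncorrected chi-square: z = [(y - x)/30] / sqrt(m(1 - m) x 2/30) >= 1.2816, with m = (x + y)/60.
- Continuity-corrected chi-square: the same, with 1/30 subtracted from the numerator.
- Fisher: pF = sum over k >= y of C(30,k) C(30,x+y-k) / C(60,x+y) <= 0.10.
- Boschloo: pF <= c, with c the largest attainable value that keeps the type I error at or below 0.10 for every common rate. At 30 per arm c = 0.1395.

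**Step 1: the plan's own table.** Fisher's test and the continuity-corrected test reject exactly the same outcomes. Their power at the five rows of Table 8-1 is 79.9%, 80.0%, 80.1%, 80.1% and 80.0%, so the table reproduces.

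**Step 2: type I error.**

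| Test | At 5% common rate | Maximum over all rates |
|---|---|---|
| Uncorrected chi-square | 11.7% | 12.3% |
| Fisher | 1.85% | 7.75% |
| Boschloo | 4.65% | 9.67% |

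At common rates of 2.5%, 10% and 20%, Fisher's type I error is 0.3%, 4.8% and 5.5%.

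**Step 3: power and detectable rates.**

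| Control v experimental | Fisher | Boschloo | Rate detectable with 80% power, Fisher / Boschloo |
|---|---|---|---|
| 2.5% v 21.8% | 79.9% | 84.9% | 21.8% / 20.0% |
| 5% v 26.7% | 80.0% | 84.4% | 26.7% / 24.9% |
| 10% v 35.5% | 80.1% | 85.6% | 35.5% / 33.0% |
| 15% v 42.4% | 80.1% | 86.5% | 42.4% / 39.3% |
| 20% v 48.1% | 80.0% | 85.1% | 48.1% / 45.5% |

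For a gain of exactly 20 points, Fisher v Boschloo: 81.9% v 86.5% at 2.5% v 22.5%; 75.3% v 80.35% at 5% v 25%; 65.0% v 71.8% at 10% v 30%. Fisher's test would need 34 per arm (68 patients) for 80% power at 5% v 25%.

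**Step 4: which results change.** Boschloo's region contains all of Fisher's and adds 14 outcomes. Examples are 3 v 0 (3/30 = 10 points), 6 v 2 (4/30 = 13.3 points) and 9 v 4 (5/30 = 16.7 points). All 14 have observed differences between 10 and 16.7 points. Every outcome with an observed difference of 20 points or more (6/30) is already significant under Fisher's test.

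**Step 5: sensitivity.** Boschloo's test has at least 80% power for a 20-point gain up to a control rate of about 5.1%; Fisher's does so up to about 3.2%. At 5% v 25%, Boschloo's power is 79.0% with 29 per arm and 79.5% with 29 control and 31 experimental patients.

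**The case against.** The plan meets its own power statement. Table 8-1 openly prints a detectable difference of 21.7 points at a 5% control rate, the target is worded as approximate, and Section 8.1 says that 20 to 28 points was used for sizing. Fisher's test and a continuity-corrected test are conventional and valid. This stands: a reader might infer from the 75.3% figure that the trial is underpowered or the table mistaken, and the documents support neither.

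The benefit may also not reach the decision. Section 8.1 calls the outcome promising if the MRD-negative rate is 20% higher. If that means an observed difference of at least 20 points, the choice between Fisher and Boschloo changes nothing: the chance of a difference that is both that large and significant is 57.0% at 5% v 25% under either test. The section does not say whether it means an observed or a true difference. The objection therefore stands under the first reading and falls under the second.

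Finally, Section 8.1.6 permits the chi-square test, which has 85.4% power at 5% v 25%, so one could say that no power is lost. Uncorrected, however, that power is bought by exceeding the 10% limit.

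**Conclusion.** The concern holds as a matter of specification and efficiency. Section 8.1.6 (i) leaves open two tests that behave differently at this sample size. The uncorrected chi-square does not respect the plan's limit, and Fisher's respects it with much to spare. Boschloo's test respects it (at most 9.67%), is never less powerful than Fisher's, and gains 4.4 to 6.4 points of power across the rows of Table 8-1.

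Two broader readings are tempting and should not be drawn. Fisher's type I error of about 2% belongs to a 5% common rate; it is higher at higher rates, up to 7.75%. And 80% power for a 20-point gain under Boschloo's test is not general. It rests on a control rate of no more than about 5% and on 30 evaluable patients per arm, with a margin of only 0.35 points at 5%. Non-evaluable patients are to be replaced (Section 8.1, populations for analysis), so final arm sizes may differ slightly.

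The figures concern the unstratified comparison only. They give no ground for demoting the stratified analysis (ii), whose size and power were not assessed here.

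**What to change.** In Section 8.1.6 (i), replace the choice of chi-square or Fisher's test by Boschloo's unconditional exact test, one-sided at 10%, as the single unstratified test. Recompute Table 8-1 with it; at 30 per arm the experimental rates become 20.0%, 24.9%, 33.0%, 39.3% and 45.5%. State in Section 8.1 whether the 20-point criterion refers to the observed or the true difference. Leave the stratified analysis (ii) as planned.

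The cost is one sentence and a five-row table, with no added patients, visits or samples. The test is in standard software but is less familiar to readers than Fisher's. Timing is the main constraint. The trial is open-label, the current version is dated September 2019, and accrual closes by 31 March 2020, so some 12-month results may already exist. The change must be made, and documented as made, before outcome data are examined. If that is no longer possible, naming Fisher's test alone would still close off the uncorrected chi-square and would agree with Table 8-1 as printed.

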- 13) Pregnancy tests must occur within 10-14 days and again within 24 hours prior to prescribing lenalidomide (prescriptions must be filled within 7 days. FCBP with regular or no menstruation must have a pregnancy test weekly for the first 28 days and then every 28 days while on therapy (including breaks in therapy); at discontinuation of lenalidomide and at Day 28 post the last dose of lenalidomide. Females with irregular menstruation must have a pregnancy test weekly for the first 28 days and then every 14 days while on therapy (including breaks in therapy), at discontinuation of lenalidomide and at Day 14 and Day 28 post the last dose of lenalidomide (see Appendix 13.6).
- 14) Serum protein electrophoresis and urine protein electrophoresis (the latter only for those whose disease is being followed by UPEP). Subjects with baseline urine protein greater than 200 mg/24 hours must have a UPEP to confirm VGPR or better. Obtain blood for M-protein levels measured by SPEP or quantitative immunoglobulins for those subjects in whom SPEP/UPEP are felt to be unreliable (IgA type multiple myeloma), depending upon which studies were positive at baseline. Response will be assessed comparing day 1 of each cycle values to the respective baseline (pre-induction treatment) values for each subject.

Assessment	Screening ²	Cycles 1-12				EOT	Long-term follow-up
		1	8	15	22		
Day	-42 to -1						

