2.2 Secondary Objectives

- Evidence of response as demonstrated by the improvement in the depth of response by at least one category according to IMWG response criteria. (For example, an improvement from very good partial response (VGPR) to near complete response (nCR) or better than nCR including conversion from CR to MRD negative disease [overall response]) at 6 and 12 months
- Progression free survival (PFS)
- Overall survival (OS)
- Duration of MRD-negative disease
- Safety and tolerability of experimental arm (IRd) vs. control arm (R)

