3.2 Secondary Endpoints

- The assessment of other measures of response including rate of VGPR, CR, sCR
- The assessment of duration of MRD-negative disease
- Estimates of PFS and OS
- Estimate of correlation between MRD status and PFS
- The assessment of safety and tolerability of IRd arm compared to R arm

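### The objective of improving response by at least one IMWG category at 6 and 12 months has no analysis: section 8.1.6 reports an at-least-PR rate that at least 60-80% of patients should already meet at entry

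*Combined protocol and SAP*

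**What the plan says.** **Objective.** Section 2.2, like the protocol summary, sets as a secondary objective "improvement in the depth of response by at least one category according to IMWG response criteria". The example in parentheses that follows ends with "conversion from CR to MRD negative disease [overall response]) at 6 and 12 months". The time points, and probably the overall-response label, belong to that objective.

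**Endpoint list.** Section 3.2 has only attained levels: "The assessment of other measures of response including rate of VGPR, CR, sCR".

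**Analysis.** Section 8.1.6 names "the overall response rate, defined as at least a partial response to therapy (>PR", then rates of at least VGPR, at least nCR, CR and sCR. Overall response gets an exact 95% binomial interval. No time point is given for any of these rates. It adds: "Duration of response will be assessed conditional upon achieving at least a partial response".

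**Reference point.** Footnote 14 of the Schedule of Events says: "Response will be assessed comparing day 1 of each cycle values to the respective baseline (pre-induction treatment) values for each subject". Section 4.5 uses the same pre-induction comparator.

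**Expected state at entry.** Section 8.1.6: "We anticipate 20-30% of pts will be high risk and 20-40% will be in less than a VGPR at study entry".

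**The concern.** At least PR is an informative threshold in patients who start untreated. These patients have completed induction and transplant, and their category is still measured from before induction. A response won earlier therefore counts as a response on study.

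The objective asks a different question: did the patient move up from where he or she entered? Section 1.9 gives better depth of response than on lenalidomide alone as part of the trial's aim. Footnote 15 of the schedule provides a marrow window for a 6-month response assessment. So the question is asked and some of the data are planned, but nothing in section 8 answers it.

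At stake is a secondary conclusion. A reader of the final report could take a high overall response rate as an effect of study treatment when most of it was present at randomisation.

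**Working it through.** The plan gives no expected rate for one-category improvement, so there is no figure of its own to reproduce for this endpoint. Its only power figures, in Table 8-1, concern MRD. Exact enumeration of a one-sided Fisher's test at alpha 0.10 with 30 per arm gives power of 0.799 to 0.801 across the five rows. This point does not alter that table.

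**1. The two definitions side by side**

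| | Sections 1 and 2.2 | Section 8.1.6 |
|---|---|---|
| Quantity | At least one category better | At least PR attained |
| Compared with | Category at study entry (implied by improvement) | Pre-induction values |
| Time | 6 and 12 months | Not stated |

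**2. Share already at least PR at entry.** Inputs: 20-40% below VGPR (section 8.1.6) and 30 patients per arm (section 8.1.1). VGPR or better implies at least PR.

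- 1 - 0.40 = 0.60, and 30 x 0.60 = 18 patients per arm
- 1 - 0.20 = 0.80, and 30 x 0.80 = 24 patients per arm

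This is a floor, because the group below VGPR can include patients in PR.

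**3. What each definition reports if no patient changes category on study** (Clopper-Pearson 95% intervals)

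- Section 8.1.6: at least 18/30 = 60% (40.6-77.3%) to 24/30 = 80% (61.4-92.3%)
- Section 2.2: 0/30 = 0% (0-11.6%)

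The zero follows from the definition. The useful number is the 60-80 points that the section 8.1.6 rate carries in from earlier treatment.

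**4. Room left for a treatment difference.** If patients at VGPR or better at entry keep at least PR, the arms can differ by at most 100 - 60 = 40 points or 100 - 80 = 20 points, and by less if many of the rest are in PR.

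**5. Duration of response.** It is conditional on at least PR and runs from the examination that confirmed the response. For the 18-24 patients per arm in step 2, that response predates randomisation.

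**6. Stratum sizes for a comparison of improvement.** By entry level alone, the group below VGPR has 30 x 0.20 = 6 to 30 x 0.40 = 12 per arm. Crossing with risk (20-30% high risk, independence assumed) leaves 30 x 0.20 x 0.20 = 1.2 to 30 x 0.40 x 0.30 = 3.6 in the smallest cell, under the limit of 5 in section 8.1.6. Stratifying on entry level only is therefore workable. At 20% below VGPR, the binomial chance of fewer than 5 among 30 is still 0.26, so the exact fallback should stay.

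**The case against.** **The label may be a slip.** The overall-response tag sits inside the example parenthesis, and section 7.9 uses the same term cumulatively from pre-induction, as section 8.1.6 does. The stray label may be the one in section 2.2. That is fair, but with the tag removed the section 2.2 objective still has no analysis.

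**The plan does measure change.** A reader might infer that no change from entry is analysed at all. The documents do not support that: the primary endpoint is conversion from MRD-positive to MRD-negative (sections 3.1 and 8.1.4). The gap concerns IMWG category. MRD conversion misses steps such as PR to VGPR.

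**Other rates show deepening.** Section 8.1.6 says the secondary objectives include its list, so the list need not be complete, and the nCR, CR and sCR rates capture part of the deepening between arms balanced on entry level. This stands in part, but those rates are not relative to each patient's own entry category.

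**The biomarker responders.** The biomarker test is justified as "given the relatively small number of responders anticipated (20" per cent). A reader might infer that its responder group is undefined. Section 8.1, item 4, expects about 20% to convert to MRD-negative, so MRD conversion is the natural reading and one clarifying phrase is enough.

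**Entry category and assay.** A reader might also doubt that sCR can be judged at entry or ask which MRD assay counts. Section 8.1.3.1 requires 10-color flow for everyone at enrolment, and sections 3.1 and 8.1.4 fix the assay by route of enrolment.

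**Conclusion.** The point holds for response category. Followed as written, section 8.1.6 would not answer the secondary objective in section 2.2. The rate it reports would mostly describe induction and transplant: at least 60-80% of patients, 18-24 of 30 per arm, meet it before the first study dose. Duration of at-least-PR response has the same weakness.

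This rests on the plan's own forecast of 20-40% below VGPR at entry, on VGPR implying at least PR, and on the pre-induction comparator in section 4.5 and footnote 14.

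A reader might infer that the comparison between arms is biased. It is not: randomisation stratified by entry level keeps the arms comparable, and the fault is that the rate answers a different question. The primary endpoint and the sample size are untouched. The change should be made, but it does not threaten the main result.

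**What to change.** **Change, in sections 3.2 and 8.1.6:**

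- Define the depth-of-response endpoint as in section 2.2: the proportion improving by at least one Appendix 14.3 category from the screening category, at 6 and at 12 months. Keep the pre-induction baseline for assigning categories. Count CR to MRD-negative by the assay used for enrolment.
- Report it by arm with exact 95% intervals. Compare the arms stratified by entry level (<VGPR vs >=VGPR), at the two-sided 5% level that section 8.1 gives for secondary analyses, with the exact logistic fallback of section 8.1.6 for small strata. Count patients without an assessment as not improved.
- Keep the at-least-PR and at-least-VGPR rates as descriptive, by entry stratum.
- Name MRD conversion as the responder definition for the biomarker analysis, if that is what the 20% means.
- Do not interpret duration of at-least-PR response for patients already at PR or better at entry. Rely on PFS and time to progression.

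**Cost.** Wording, plus one derived variable: the full screening category, for which section 4.2.1 already requires the blood and urine tests. There are three downsides:

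1. The 6-month marrow is conditional on a recorded CR, with a 3-9 month window. Upgrades to CR or deeper at 6 months will be incompletely ascertained, so the 12-month result should carry the main weight.
2. After screening, section 4.2.2 requires only the tests used to follow each patient's disease until a response is to be confirmed. Appendix 14.3 asks for serum and urine studies for VGPR and CR. Some upgrades will therefore depend on the confirmatory set.
3. Counting missing assessments as not improved lowers the rate in both arms.
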